6.2.2.2. Data Handling Rules

For ELISpot, values below the positivity threshold will be imputed with half of the threshold.

For the calculation of fold increases, ELISpot values below the positivity threshold will be imputed with the threshold. Fold increases will not be calculated for ICS.

6.2.2.3. Analysis Methods

The cellular immune responses will be evaluated separately for each part of the study. Within each part, the data will primarily be presented by vaccination schedule with a distinction between the healthy and HIV-infected cohorts. The cellular data will not be presented by age stratum. Also, the cellular data for healthy and HIV-infected cohorts will not be combined for analysis. See [Table 4](#) for details.

Summary statistics (ie, median, quartiles [Q1, Q3]) will be presented for all continuous cellular immunogenicity outcomes (ie, ELISpot and ICS) at each time point. Also, the median fold increases (from Pre-dose 1 and Pre-dose 2) with the corresponding quartiles (Q1 and Q3) will be presented for ELISpot only.

Graphical representations (on a \log_{10} -scale) will be provided using dot plots, by vaccination schedule. Also, regimen profiles of the vaccination schedules showing the median and the quartiles (Q1 and Q3) will be presented. Other profiles (median and quartiles) will be generated by pre-existing antibody response against Ad26 vector (ie, pre-existing Ad26 versus not pre-existing Ad26 vector). Responder and positive sample interpretation rates will be summarized

(ie, showing number, percentage and the corresponding exact 95% Clopper-Pearson CIs) per timepoint.

For ICS, the proportions of EBOV GP-specific CD4+ and CD8+ T cells (ie, cells producing at least 1 of the 3 investigated cytokines) will also be tabulated per timepoint and shown in a pie chart. The magnitude of each cytokine subset will be shown in a bar chart. Both pie chart and bar chart will be restricted to responders.

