2. OBJECTIVES AND HYPOTHESIS

2.1. Objectives

Primary Objectives

The primary objectives are:

- To assess the safety and tolerability of different vaccination schedules of Ad26.ZEBOV and MVA-BN-Filo administered IM as heterologous prime-boost regimens in healthy and in HIV-infected adults, with Ad26.ZEBOV prime and MVA-BN-Filo boost vaccination on Days 1 and 29, respectively and MVA-BN-Filo prime and Ad26.ZEBOV boost vaccination on Days 1 and 15, respectively.
- To assess the immune responses to the EBOV GP (as measured by ELISA antibody concentration) of different vaccination schedules of Ad26.ZEBOV and MVA-BN-Filo administered IM as heterologous prime-boost regimens in healthy and in HIV-infected adults, with Ad26.ZEBOV prime and MVA-BN-Filo boost vaccination on Days 1 and 29, respectively and MVA-BN-Filo prime and Ad26.ZEBOV boost vaccination on Days 1 and 15, respectively.

Secondary Objective

To compare safety and tolerability of both Ad26.ZEBOV/MVA-BN-Filo and MVA-BN-Filo/Ad26.ZEBOV regimens between healthy and HIV-infected adults.

Exploratory Objectives

The exploratory objectives include the following. Some exploratory objectives may not be performed if reagents or assays are not available.

- To assess the humoral immune responses further regarding kinetics and durability as well as neutralizing antibody responses directed against EBOV GP induced by the heterologous prime-boost regimen as measured by a virus neutralization assay, at relevant time points of different vaccination schedules of Ad26.ZEBOV and MVA-BN-Filo.
- To assess the kinetics and durability of cellular immune responses in healthy and HIV-infected adults for EBOV GP, by vaccine regime.
- To compare kinetics and durability of humoral and cellular immune responses to EBOV GP of Ad26.ZEBOV/MVA-BN-Filo and MVA-BN-Filo/Ad26.ZEBOV regimens between healthy and HIV-infected adults.
- To assess the kinetics and durability of humoral immune responses, including the development of neutralizing antibodies, in healthy and HIV-infected adults for other filovirus GP.
- To assess the kinetics and durability of cellular immune responses in healthy and HIV-infected adults for other filovirus GP.
- To compare kinetics and durability of humoral and cellular immune responses to other filovirus GP, of Ad26.ZEBOV/MVA-BN-Filo and MVA-BN-Filo/Ad26.ZEBOV regimens between healthy and HIV-infected adults.

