- To assess the frequency, magnitude, and durability of anti-vector responses in healthy and HIV-infected adults.
- To compare kinetics and durability of humoral and cellular immune responses to the EBOV and other filovirus GP of Ad26.ZEBOV/MVA-BN-Filo and MVA-BN-Filo/Ad26.ZEBOV regimens between adults aged 18-50 and aged 51-70.
- To assess the impact of CD4+ count on safety and immunogenicity of Ad26.ZEBOV/MVA-BN-Filo and MVA-BN-Filo/Ad26.ZEBOV regimens in HIV-infected adults.
- To assess changes in HIV RNA and HIV specific immune response (using HIV antigens in place of Ebola GP) associated with vaccination with Ad26.ZEBOV/MVA-BN-Filo and MVA-BN-Filo/Ad26.ZEBOV regimens in HIV-infected adults.
- To assess humoral immune responses in genital, rectal and oral secretions in a subset of healthy and HIV-infected adults at selected sites for EBOV and other filovirus GP.
- To explore the impact of host genetics on immune responses to the Ad26.ZEBOV/MVA-BN-Filo and MVA-BN-Filo/Ad26.ZEBOV prime-boost regimens in healthy and HIV-infected adults.
- To assess immune epitope breadth elicited by the Ad26.ZEBOV/MVA-BN-Filo and MVA-BN-Filo/Ad26.ZEBOV prime-boost regimens in healthy and HIV-infected adults.
- To assess the immunoglobulin subclass, glycosylation and effector functions of humoral responses to EBOV and other filovirus GP.

- To describe B cell, helper T cell, and cytotoxic T cell responses elicited by the Ad26.ZEBOV/MVA-BN-Filo and MVA-BN-Filo/Ad26.ZEBOV prime-boost regimens in healthy and HIV-infected adults.
- To explore immune inflammatory responses elicited by the Ad26.ZEBOV/MVA-BN-Filo and MVA-BN-Filo/Ad26.ZEBOV regimens in healthy and HIV-infected adults on a multiplex array platform to evaluate cytokine and soluble factor responses to vaccination.

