9.2.3. Exploratory Endpoints

Additional exploratory analyses may be performed to further investigate study vaccine-elicited immune responses. The exploratory endpoints might include but are not limited to the following:

- Magnitude, kinetics and durability of humoral immune responses to EBOV GP, including neutralizing antibody response measured in titers that inhibit viral infection by a certain percentage (IC_{50, 80 or 90}).
- Magnitude, kinetics and durability of cellular immune responses for EBOV GP (EBOV GP specific T cell responses will be measured as the number of IFN- γ producing cells by ELISpot analysis).
- Comparison between healthy and HIV-infected adults of the kinetics and durability of humoral and cellular immune responses to EBOV GP of Ad26.ZEBOV/MVA-BN-Filo and MVA-BN-Filo/Ad26.ZEBOV regimens.
- Kinetics and durability of humoral immune responses, including the development of neutralizing antibodies, in healthy and HIV-infected adults for other filovirus GP (binding antibody response measured in ELISA units/mL and/or endpoint-titers; neutralizing antibody response measured as titers that inhibit viral infection by a certain percentage [IC_{50, 80 or 90}]).
- Kinetics and durability of cellular immune responses in healthy and HIV-infected adults for other filovirus GP (EBOV GP specific T cell responses will be measured as the number of IFN- γ producing cells by ELISpot analysis or the percentage of CD4+ or CD8+ T cells producing IFN- γ , tumor necrosis factor- α (TNF- α) and/or interleukin (IL)-2 by intracellular cytokine staining [ICS]).
- Comparison of kinetics and durability of humoral and cellular immune responses to the other filovirus GP, of Ad26.ZEBOV/MVA-BN-Filo and MVA-BN-Filo/Ad26.ZEBOV regimens between healthy and HIV-infected adults.
- Comparison of kinetics and durability of humoral and cellular immune responses to the EBOV other filovirus GP of Ad26.ZEBOV/MVA-BN-Filo and MVA-BN-Filo/Ad26.ZEBOV regimens between adults aged 18-50 and aged 51-70.
- Frequency, magnitude, and durability of anti-vector responses in healthy and HIV-infected adults (measured by ELISA, virus neutralization assay [VNA] and/or plaque reduction neutralization test [PRNT]).
- Time course of CD4+ count in HIV-infected adults.

- Changes in HIV RNA and HIV specific immune response (using HIV antigens in place of Ebola GP) associated with vaccination with Ad26.ZEBOV/MVA-BN-Filo and MVA-BN-Filo/Ad26.ZEBOV regimens in HIV-infected adults.

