11.5. Immunogenicity Analyses

The primary immunogenicity endpoint in Part 1 and Part 2 is the Day 21 post-boost visit. Immunogenicity analyses will be conducted during the planned interim analyses and the final analysis. In addition, immunogenicity analyses may be conducted during ad hoc interim analyses. For more details about the interim and final analyses, see Sections 11 and 11.6. Within each part, the HIV-infected groups will be analyzed separately and in comparison with the healthy groups.

Descriptive statistics (actual values and changes from baseline, including 95% confidence intervals, if applicable) will be calculated for continuous immunologic parameters by time point. Graphical representations of changes in immunologic parameters will be prepared, as applicable. Frequency tabulations will be calculated for discrete (qualitative) immunologic parameters by time point. Response patterns over time for the immunologic parameters will be analyzed, taking into account within-subject correlations, to describe differences between the vaccination schedules at 21 days post-boost, 42 days post-boost, 6 months post-boost and 1 year post-boost.

Immunogenicity endpoints will be compared between treatment groups, in particular ELISA levels for Part 2. Immunogenicity data will be compared between vaccine groups for healthy and HIV-infected groups separately and combined. The immunogenicity data will also be compared between the healthy and HIV-infected groups within each vaccination group and across vaccination groups.

Details on the statistical analysis of the immunogenicity data will be provided in the SAP.

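### The SAP rules out any age split for ELISpot and ICS, so the cellular half of the protocol's exploratory 18-50 versus 51-70 comparison gets no estimate, and no reason is recorded

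*SAP*

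**What the plan says.** **Protocol.** The exploratory objectives in 2.1 include "To compare kinetics and durability of humoral and cellular immune responses to the EBOV and other filovirus GP of" the two regimens, and the groups to be contrasted are given as "regimens between adults aged 18-50 and aged 51-70". Section 9.2.3 carries the same item as an exploratory endpoint: "Comparison of kinetics and durability of humoral and cellular immune responses to the EBOV other filovirus GP of" the two regimens, by the same two age groups. Two qualifications come with these lists. The objectives are introduced with "Some exploratory objectives may not be performed if reagents or assays are not available", and the endpoints with "The exploratory endpoints might include but are not limited to the following". Protocol 11.5 plans no by-age cellular analysis of its own and defers to the SAP: "Details on the statistical analysis of the immunogenicity data will be provided in the SAP". Protocol 5 stratifies the randomisation at age 50.

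**SAP.** Section 2.4 and Table 4 attach only ELISA and VNA to the 18-50 and 51-70 rows. ELISpot and ICS appear only for 18-70. A note to Table 4 says that no VNA is currently available for HIV-infected subjects. Section 6.2.2.3 makes the exclusion explicit: "The cellular data will not be presented by age stratum". The same paragraph keeps the healthy and HIV-infected cohorts separate for cellular data. Section 3 lists three departures from the planned analysis: the immunogenicity set, the per protocol set and the antiretroviral adherence analysis. None concerns age or cellular data, and the SAP amendment history does not mention the point either.

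**The concern.** The protocol commits, at exploratory level, to describing how cellular responses differ by age, and the SAP removes that description without saying so in the section meant for departures. The assay-availability condition does not explain the removal, because the SAP still summarises ELISpot and ICS over the whole 18-70 range where those results exist.

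The age range matters to this study. The protocol's section on potential risks (1.2.4) says that neither vaccine has clinical data in adults over 50, and its rationale (1.3) names extension to age 70 as a purpose of the trial. Under the SAP as written, any age difference in T-cell response is absorbed into the 18-70 figure, and the report offers no cellular estimate for the older stratum.

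**Working it through.** **1. Text check.** By-age output planned for the responses named in the objective:

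| Response | Named in the protocol age comparison | By-age output in SAP 2.4 / Table 4 |
|---|---|---|
| ELISA | yes (humoral) | yes, both cohorts |
| VNA | yes (humoral) | yes, healthy subjects; no assay yet for HIV-infected |
| ELISpot | yes (cellular) | no |
| ICS | yes (cellular) | no |

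Entries in SAP 3 that cover the two missing rows: 0 of 3.

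**2. Do the escape clauses cover it?** Protocol 2.1 releases an exploratory objective when reagents or assays are lacking. SAP 1.1 and 6.1 make the objectives depend on the outcome being available. The bar in SAP 6.2.2.3 carries no such condition: it applies even when ELISpot and ICS results exist. The variable is also at hand, since age group is a randomisation stratum and a tabulated baseline characteristic (SAP 1.5, 5.3). Nor does 6.2.2.3 avoid subgroup displays for cellular data in general, because it plans profiles by pre-existing Ad26 antibody.

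**3. What precision would an age split have?** The plan gives no figure to reproduce, and the number of subjects over 50 is not stated. I assume a share of 10-25%, which is not from the documents.

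The base must be a single cohort, because 6.2.2.3 does not allow the cohorts to be combined. Active subjects per cohort (Protocol Table 1, SAP Table 1) are 160 in Part 2 Group 1 and 40 in Group 2. Placebo subjects per cohort are 40 and 10.

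- Group 1 active, over 50: 0.10 × 160 = 16 to 0.25 × 160 = 40.
- Group 2 active, over 50: 0.10 × 40 = 4 to 0.25 × 40 = 10.
- Group 1 placebo, over 50: 0.10 × 40 = 4 to 0.25 × 40 = 10.
- Group 2 placebo, over 50: 0.10 × 10 = 1 to 0.25 × 10 = 2.5.

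Exact 95% Clopper-Pearson limits for x responders out of n are the 2.5% quantile of Beta(x, n − x + 1) and the 97.5% quantile of Beta(x + 1, n − x). At an observed 50% responder rate:

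| Responders / n | Exact 95% interval | Half-width, points |
|---|---|---|
| 8/16 | 24.7% to 75.3% | about 25 |
| 20/40 | 33.8% to 66.2% | about 16 |
| 5/10 | 18.7% to 81.3% | about 31 |
| 2/4 | 6.8% to 93.2% | about 43 |

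For the difference between age groups within one Group 1 cohort, the normal approximation at 50% in both gives a half-width of 1.96 × √(0.25/n₁ + 0.25/n₂):

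- 16 versus 144: 1.96 × √(0.015625 + 0.001736) = 0.258, about 26 points.
- 40 versus 120: 1.96 × √(0.00625 + 0.002083) = 0.179, about 18 points.

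**The case against.** The strongest case for leaving the SAP alone has four parts.

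*The item is exploratory.* It is one of many. The endpoint list is permissive, the SAP says that the cellular assays may be analysed, and no formal testing is planned (Protocol 2.2, SAP 1.2). This stands, and it limits the weight of the point. It does not turn an unconditional, unexplained exclusion into a consequence of assay availability.

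*Protocol 11.5 leaves the detail to the SAP,* so a sponsor can argue that nothing planned was changed, and Protocol 17.13 allows exploratory results in a later separate report. That is arguable. Even so, neither clause tells a reader that this comparison was dropped or why, whereas SAP 3 does record another dropped analysis (antiretroviral adherence) with its reason.

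*The over-50 cells may be too small to be useful.* This largely holds for Group 2 and for placebo, as the intervals above show. For active recipients in Group 1 it is a reason for caution in reading the summaries and does not justify omitting them.

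*Recording the omission would be enough.* A justified entry in SAP 3 would remove the inconsistency, but it would leave the cellular comparison undescribed when the split is cheap.

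Three stronger readings are tempting, and the documents do not support them.

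- A reader might infer that the whole age objective goes unanswered. It does not: ELISA is reported by age in both cohorts, and VNA by age in healthy subjects.
- A reader might infer that over-50 T-cell results exist for all 575 planned subjects at six visits. The documents schedule blood collection and do not establish assay results. Placebo subjects may also finish at unblinding without a 1-year visit (Protocol 3.1).
- A reader might take all 320 active Group 1 subjects as the base for precision. That pools cohorts which SAP 6.2.2.3 keeps apart.

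**Conclusion.** The inconsistency is real and limited in scope. The protocol names a cellular age comparison as an exploratory objective and endpoint, the SAP bars it outright for ELISpot and ICS, and no change or reason is recorded. The humoral half is reported by age, and the primary and secondary objectives are untouched.

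The text finding rests on no numerical assumption. The precision statement rests on an assumed over-50 share of 10-25%. On that assumption, a by-cohort responder rate among active Group 1 recipients over 50 would be known to within about 16 to 25 points, which is enough to describe only large age differences. Group 2 and placebo cells would be close to uninformative. The change is still worth making, because the data would otherwise be summarised only in aggregate for an age range in which the protocol says there is no clinical experience.

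**What to change.** Delete the sentence "The cellular data will not be presented by age stratum" from SAP 6.2.2.3. Add ELISpot and ICS, where results are available, to the by-cohort 18-50 and 51-70 rows that already exist in Table 4. Report n, median, Q1, Q3 and the responder rate with its Clopper-Pearson interval. Apart from n, these are statistics that 6.2.2.3 already specifies for cellular data. Keep the presentation descriptive, centre it on active recipients in Part 2 Group 1, and do not combine the healthy and HIV-infected cohorts. Where cells are very small, as expected in Group 2 (about 4 to 10 active subjects over 50 per cohort on the assumed share) and in placebo, listings can replace summaries.

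If the sponsor decides against the split, the minimum is an entry in SAP 3 that states the omission and the reason for it.

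The cost is a few extra tables from existing data, plus very wide intervals in the small cells, which should be labelled as such.

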6.3. Immunogenicity Against the Vector

6.3.1. Humoral Immune Responses

6.3.1.1. Parameter

Immune responses, as measured by the Ad26 VNA (serum titers of neutralizing antibodies to the Ad26 vector [IC₉₀]) will be analyzed. The following will also be defined for Ad26 VNA titers:

Sample interpretation: a sample will be considered positive, if the value is above the assay-specific LLOQ.

6.3.1.2. Data Handling Rules

For the outcome (ie, Ad26 VNA), values below the LLOQ will be imputed with half of the LLOQ (LLOQ/2).

6.3.1.3. Analysis Methods

The humoral immune responses (ie, immunogenicity against Ad26 vector) will be evaluated separately for each part of the study. Within each part, the data will primarily be presented by cohort (ie, healthy and HIV-infected) and vaccination schedule.

The geometric mean and corresponding 95% CIs will be calculated. Positive sample interpretation will be summarized (ie, showing number, percentage and the exact 95% Clopper-Pearson CI). A data listing will also be generated.

7. SAFETY

The safety and tolerability data include the following:

- AEs (unsolicited AEs) collected from signing of the informed consent form (ICF) onwards until the 42-day Post-dose 2 visit.
- Serious adverse events (SAEs) and immediate reportable events (IREs) collected from signing of the ICF onwards until the end of the study.
- Solicited local and systemic AEs (reactogenicity) collected until 7 days after each administration of study vaccine.

The safety and tolerability data will be summarized based on the full analysis set. The analysis will be based on the actual dose (ie, dose 1 and dose 2 for the first and second vaccinations,

respectively) that the subjects received. For example, if dose 2 is not administered to a subject, then that subject will not be included in the analysis of AEs in the Post-dose 2 period. Focus will be on safety signals detected during the Post-dose 1 and Post-dose 2 periods, as well as the Regimen period (ie, combined Post-dose 1 and Post-dose 2 periods).

In general, safety data will be evaluated separately for each part of the study. Within each part, the data will primarily be presented by cohort (healthy and HIV-infected) and by vaccination schedule. Secondly, the data from Parts 1 and 2 of the study will be pooled (ie, 14-day interval regimen) and presented separately for the healthy and HIV-infected cohorts. See [Table 4](#) for a schematic overview the subgroups to be considered for the safety analysis.

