11.1. Sample Size Determination

An overall planned sample size of 575 subjects includes 460 subjects who will receive active prime-boost vaccination to substantially contribute to an overall safety database of the Ad26.ZEBOV and MVA-BN-Filo prime-boost regimen.

In Part 1, a total of 60 subjects (40 healthy and 20 HIV-infected) are planned to be vaccinated with MVA-BN-Filo prime vaccination followed by Ad26.ZEBOV 14 days later.

In Part 2, Group 1, a total of 320 subjects (160 healthy and 160 HIV-infected) will be vaccinated with Ad26.ZEBOV on Day 1, followed by MVA-BN-Filo 28 days later and in Group 2, a total of

80 subjects (40 healthy and 40 HIV-infected) will be given MVA-BN-Filo prime vaccination followed by Ad26.ZEBOV 14 days later.

The sample size is based on the probability of observing an adverse event given the true underlying incidence and is described in Table 4. In case a specific adverse event is not observed, the one-sided 97.5% upper confidence limit of the true incidence rate of this adverse event is less than 16.8%, 8.8%, 6.0%, 4.5%, 2.3%, 1.5%, 1.1%, and 0.8% for a total of 20, 40, 60, 80, 160, 240, 320, and 460 subjects on Ad26.ZEBOV and MVA-BN-Filo, respectively. Note that this does include some scenarios based on combining the data from Part 1 and Part 2. An analysis that combines data from Part 1 and Part 2 is appropriate for estimating safety parameters although any formal comparisons between vaccination regimens or HIV cohorts would likely only consider data from Part 2 of the study.

Table 4: Probability of Observing at Least One Adverse Event Given a True Adverse Event Incidence

| True Adverse Event Incidence | N=20 | N=40 | N=60 | N=80 | N=160 | N=240 | N=320 | N=460 |
|-------------------------------------|-------------|-------------|-------------|-------------|--------------|--------------|--------------|--------------|
| 0.1% | 2.0% | 3.9% | 5.8% | 7.7% | 14.8% | 21.4% | 27.4% | 36.9% |
| 0.5% | 9.5% | 18.2% | 26.0% | 33.0% | 55.2% | 70.0 | 79.9% | 90.0% |
| 1% | 18.2% | 33.1% | 45.3% | 55.3% | 80.0 | 91.0% | 96.0% | 99.0% |
| 2.5% | 39.7% | 63.7% | 78.1% | 86.8% | 98.3% | 99.8% | 100% | 100% |
| 5% | 64.2% | 87.2% | 95.4% | 98.4% | 100% | 100% | 100% | 100% |
| 10% | 87.8% | 98.5% | 99.8% | 100% | 100% | 100% | 100% | 100% |

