11.2. Analysis Sets

The Full Analysis set includes all subjects who were randomized and received at least 1 dose of study vaccine, regardless of the occurrence of protocol deviations. Safety data will be analyzed based on the Full Analysis set.

The Immunogenicity Analysis set includes all randomized and vaccinated subjects, who have data from baseline and at least 1 post-vaccination immunogenicity blood draw.

The Per Protocol Analysis set includes all randomized and vaccinated subjects, who received both the prime and boost vaccinations (administered not more than 10 days outside the visit window), have immunogenicity data from baseline and at least 1 post-vaccination evaluable immunogenicity sample, and have no major protocol violations influencing the immune response.

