The verbatim terms used in the CRF by investigators to report adverse events will be coded using the Medical Dictionary for Regulatory Activities (MedDRA). All reported adverse events (solicited local, solicited systemic, and unsolicited) will be included in the analysis. For each adverse event, the number and percentage of subjects who experience at least 1 occurrence of the given event will be summarized by group. Summaries, listings, datasets and/or subject narratives may be provided as appropriate, for those subjects who die, discontinue study vaccinations due to an adverse event, or experience a severe or serious adverse event. The analysis for solicited adverse events will be done on those subjects in the Full Analysis set for whom reactogenicity assessments are available in the database. The analysis of unsolicited adverse events will be done based on the Full Analysis set.

Physical Examination

Physical examination abnormalities will be listed. BMI will be calculated using the recording of height at screening.

Vital signs

Vital signs abnormalities will be tabulated by worst abnormality grade.

Clinical Laboratory Tests

Laboratory abnormalities will be determined in accordance with Toxicity Table for Use in Trials Enrolling Healthy Adults ([Attachment 2](#)). Laboratory abnormalities will be tabulated per treatment group by worst abnormality grade.

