3. CHANGES TO THE PLANNED ANALYSIS

- Even in the absence of baseline immunogenicity samples, the post-baseline samples are of interest. Therefore, the immunogenicity analysis set is redefined to include subjects without baseline immunogenicity samples, provided that at least 1 post-vaccination (ie, after the date of vaccination) evaluable immunogenicity sample is available for the subjects.
- Because different levels of Post-dose 2 immune responses are expected for different vaccination schedules, the per protocol analysis set is redefined to exclude subjects whose second vaccination falls outside the protocol-defined window. Similar to the immunogenicity analysis set, the per protocol analysis set is also refined to include subjects without baseline immunogenicity samples
- Because of the lack of the necessary data to assess non-adherence, the planned additionally analysis restricted to HIV-infected subjects who adhere to antiretroviral therapy (ART) if more than 10% of the HIV-infected subjects exhibit non-adherence to ART will not be performed.

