7.1.2. Data Handling Rules

Missing data will not be imputed. If severity or relationship of AEs to the study vaccine could not be derived (ie, missing or unknown), it will be considered as unknown, for analysis purposes. Local solicited AEs will be considered as related with the use of the study vaccine, by definition.

Solicited events will always be allocated to the analysis period (Section 2.1). For analysis purpose, the AEs will be allocated to periods and/or phases as described in Attachment 2.1.

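### SAP 7 summarizes solicited adverse events on the whole full analysis set, Protocol 11.4 only on subjects with reactogenicity assessments, and SAP 3 declares no change

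*SAP*

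**What the plan says.** Protocol 11.2 gives the general rule: "Safety data will be analyzed based on the Full Analysis set". Protocol 11.4, under adverse events, then treats the two kinds of event differently. The analysis of "solicited adverse events will be done on those subjects in the Full Analysis set for whom reactogenicity assessments are available in the database". The next sentence reads: "The analysis of unsolicited adverse events will be done based on the Full Analysis set".

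SAP 7 lists three kinds of safety data, the third being "Solicited local and systemic AEs (reactogenicity) collected until 7 days after each administration of study vaccine". For all of them it says: "The safety and tolerability data will be summarized based on the full analysis set". SAP 2.3 defines that set as everyone randomized who received at least one dose, with no condition on available data. SAP 7 does limit the denominator in one way: a subject who did not receive dose 2 is left out of the Post-dose 2 adverse-event analysis.

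On missing data, SAP 7.1.2 says "Missing data will not be imputed" and sets no denominator. SAP Attachment 2 treats a day without data as a day without an event.

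SAP 3 lists three changes to the planned analysis. One is that "the immunogenicity analysis set is redefined to include subjects without baseline immunogenicity samples". The others redefine the per protocol set and drop an analysis restricted to subjects adherent to antiretroviral therapy. None concerns solicited events.

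**The concern.** Solicited local and systemic events are a primary endpoint (Protocol 9.2.1), reported as the number and percentage of subjects with at least one occurrence (Protocol 11.4). The numerator is the same under both documents, because a subject with no assessment cannot contribute an event. The denominator can differ. Under the SAP as written, a vaccinated subject with no reactogenicity data is counted as having had no reaction, so the percentage can only stay the same or fall. Two programmers, one working from each document, could produce different primary-endpoint percentages from the same data. The smallest cells are the most exposed: the Part 1 HIV-infected cohort has 20 active and 5 placebo subjects (Protocol Table 1).

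**Working it through.** **1. The plan's own figure.** No solicited-event percentage or missing-diary rate is stated, so there is none to reproduce. The one related figure is in Protocol 11.1: if an event is not observed, "the one-sided 97.5% upper confidence limit of the true incidence rate of this adverse event is less than 16.8" percent for 20 subjects. The formula is 1 − 0.025^(1/n). It gives 16.84% at n = 20, 8.81% at n = 40 and 2.28% at n = 160, which agrees with the protocol's 16.8%, 8.8% and 2.3%.

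**2. Direction.** Let r be the subjects with at least one solicited event after a dose, n the subjects who received that dose, and x those among them with no reactogenicity assessment.

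- Protocol 11.4 percentage: p = r/(n − x)
- SAP 7 percentage, read literally: r/n = p(1 − x/n)
- Fall in points: p·x/n
- Relative fall: x/n

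So r/n is never above r/(n − x), and the two are equal when x = 0 or r = 0.

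**3. Size.** x is not in the documents, so 0, 1 and 2 are assumed. At x = 0 the fall is zero everywhere. The relative fall needs no assumed event rate. The fall in points is shown at p = 50% and p = 78%, the shares with a local reaction after the first dose in the first-in-human study (Protocol 1.1). These rates are illustrations only: they come from blinded groups that mix vaccine and placebo recipients.

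| n (planned active cell) | x | relative fall x/n | points at p = 50% | points at p = 78% |
|---|---|---|---|---|
| 20 (Part 1, HIV-infected) | 1 | 5% | 2.5 | 3.9 |
| 20 | 2 | 10% | 5.0 | 7.8 |
| 40 (Part 1 healthy; each Part 2 Group 2 cohort) | 1 | 2.5% | 1.3 | 2.0 |
| 40 | 2 | 5% | 2.5 | 3.9 |
| 160 (each Part 2 Group 1 cohort) | 1 | 0.6% | 0.3 | 0.5 |
| 160 | 2 | 1.3% | 0.6 | 1.0 |

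For example, at n = 20 and p = 78%, 0.78 × 1/20 = 3.9 points. In whole subjects, 15/19 = 78.9% becomes 15/20 = 75.0%. In placebo cells, one unassessed subject gives a relative fall of 1/5 = 20% or 1/10 = 10%.

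**4. Confidence limits.** For a reaction never observed, the upper limit should rest on the subjects actually assessed:

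- n = 20: 16.8% becomes 17.6% with 19 assessed and 18.5% with 18.
- n = 40: 8.8% becomes 9.0% with 39 and 9.3% with 38.
- n = 160: it stays at 2.3%.

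When reactions occur, the literal SAP denominator moves both exact limits down, but the width can go either way:

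| protocol denominator | width (points) | SAP denominator | width (points) |
|---|---|---|---|
| 5/19 | 42.1 | 5/20 | 40.5 |
| 15/19 (54.4 to 93.9%) | 39.5 | 15/20 (50.9 to 91.3%) | 40.4 |
| 17/19 | 31.8 | 17/20 | 34.7 |

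**The case against.** The strongest reply is that this is an omission and not a change of plan. The SAP 7 sentence is close to Protocol 11.2, and the protocol itself holds that general rule alongside the 11.4 exception. The no-imputation rule in SAP 7.1.2 could also be read as barring anyone from treating a wholly unassessed subject as reaction-free. The practical effect may also be nil. Subjects are observed on site for about 30 minutes after each dose and solicited events seen there are recorded (Protocol 9.3.1). They return at 7 days for diary review and injection-site examination (Protocol 9.1.3), and SAP Attachment 2 counts on-site assessments within 8 days. If those checks count as available assessments, nearly every dosed subject qualifies and the two denominators coincide. No formal hypothesis is tested (SAP 1.2), so no decision rule is affected.

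Much of this stands. Omission is a plausible explanation, and the effect is probably near zero in the larger cells. The gap in the text remains. The protocol sets two different populations in adjacent sentences, which is a deliberate distinction. The SAP names solicited events and then applies only the general rule. Its one stated limit concerns receipt of dose 2, not availability of data. Its no-imputation rule does not say who is counted, and the day-level rule in Attachment 2 points the other way.

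A reader might infer more than the documents support:

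- **That the primary endpoint is materially understated.** No number of unassessed subjects is given, and the visit schedule suggests few.
- **That confidence intervals become too narrow.** That holds for absent or less common reactions. At 15/19 or 17/19 the literal SAP interval is slightly wider. SAP 7.1.3 names no interval for adverse-event percentages, and SAP 2 asks for intervals only where applicable.
- **That the missing-day rule in Attachment 2 is part of the error.** It is an explicit SAP rule that does not conflict with Protocol 11.4, and it is a separate matter.

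**Conclusion.** The conflict holds. The SAP omits the protocol's restriction on the solicited-event denominator, and SAP 3 does not declare a change. The direction is certain for the literal reading: the percentage is lowered by a relative x/n or left unchanged. The size is unknown and probably small. One unassessed subject gives a relative fall of 5% in the smallest active cell and 0.6% in the largest, and none gives no change. The upper limit for a reaction never seen at n = 20 would be reported as 16.8% instead of 17.6% when x = 1. All sizes rest on assumed values of x and, for points, on illustrative Phase 1 rates. The point merits correction because it touches a primary endpoint and is cheap to settle. It does not show that any reported rate will be misleading.

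**What to change.** In SAP 7 or 7.1.3, state that solicited-event percentages use, for each post-dose period, the full-analysis-set subjects who received that dose and have reactogenicity assessments in the database for it. Show that number in each solicited-event table. Protocol 11.4 does not say that the condition applies dose by dose. That is the natural reading, because the SAP presents results by period, but the sentence should make it explicit and should say whether on-site checks alone count as an assessment. If the whole full analysis set is intended instead, list and justify it in SAP 3.

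The cost is one sentence, a denominator flag for each dose and one extra count per table. No new data are needed. Compared with the literal SAP rule, percentages stay the same or rise slightly.
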